In this study, we aim, first, to estimate the effectiveness of nonpharmaceutical interventions on SARS-COV2 transmission and COVID-19 mortality in Latin America; second, to examine the effect heterogeneity of transmission and mortality at the local level. Third, assuming we find evidence of moderate to substantial heterogeneity at the local level, we aim to explore potential explanations for this heterogeneity. We will use an interrupted time series method to estimate their effects in each local government, and random effects meta-analysis and meta-regression to obtain pooled effects, heterogeneity estimates and potential explanations.

Methods

Design and setting

The study is a natural experiment where we exploit the variation in the temporal and spatial implementation of policy interventions, aimed to reduce the spread and mortality of COVID-19 in Latin America. The unit of analysis are local governments, i.e. third-tier administrative levels such as municipalities, districts or cantons.

We will include all countries fulfilling the following eligibility criteria: (1) Spanish or Portuguese speaking countries in Latin America, and (2) availability of open data at the subnational level for either of the outcomes. Appendix I presents the eligible countries, the exclusion criteria and the sources of data for each excluded country. To date, eligible countries are Argentina, Brazil, Chile, Colombia, Costa Rica, Guatemala, Mexico, Paraguay, and Peru. These countries represent 80.9%

of the population in Latin America, and the vast majority of SARS-CoV-2 cases and COVID-19 deaths.

Interventions

We will examine the impact of several interventions to tackle the COVID-19 pandemic. These interventions include (i) policies aimed at reducing viral transmission, (ii) policies aimed at increasing the capacity of the health system's response, and (iii) policies aimed at mitigating the negative consequences of the epidemic and potential adverse effects of interventions. We will use the PoliMap taxonomy to categorise the examined policies.¹⁸ Table 1 describes the policy interventions in each policy domain included in the study.

Table 1. Policy interventions included in the study

Domain	Policy interventions

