The first model at the local level does not include covariates (see below). The second model (i.e. the meta-analysis), we will examine the change in heterogeneity after adjusting for several covariates at the local level. Local level covariates include projected population size in 2020, demographic density, age-structure of the population, household density and socioeconomic status. We will use data from official sources of information, primarily the latest national population census in each included country.

Statistical analysis

The Statistical Analysis Plan provides details on the modelling assumptions. We will use an interrupted time series design, where each local government acts as its own control.^{20,21} The main

strength of this design is its capacity to distinguish the effect of the intervention from secular change.²² We will use a Poisson regression to model the count data (for both outcomes) and accounting for overdispersion and secular trends.²³ A full discussion on potential biases and violations of assumptions can be found in the Statistical Analysis Plan.

In a second stage, we will use random effects meta analysis to pool the effect estimates for each intervention or combination of interventions. This analysis informs whether any implemented intervention was effective to reduce COVID-19 cases and deaths and the degree of heterogeneity between the effects at the local level. If we observe high levels of heterogeneity (defined as higher than 50%), we will also use standard meta-regression techniques to assess whether local level determinants (see *Covariates*) can explain the observed heterogeneity.

We will build the models and test the analytical strategy using publicly available data on COVID-19 cases and deaths from Finland and Sweden from January 1 to March 31.

References

2. United Nations Department of Economic and Social Affairs. World Social Report 2020: Inequality in a rapidly changing world. New York, United States: United Nations; 2020.
3. World Health Organization. Report of the WHO-China Joint Mission on Coronavirus Disease 2019 (COVID-19)2020. <https://www.who.int/docs/default-source/coronaviruse/who-china-joint-mission-on-covid-19-final-report.pdf> (accessed March 26, 2020).

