Assumption 2. We will explicitly incorporate co-occurring interventions in a seven-day period as a combination of interventions. We will also adjust for changes in the case definition of COVID-19 cases and deaths for each of the respective outcomes. We will report in the Supplementary Appendix the exact dates considered in the analysis for each country/subnational unit and the interventions included in each intervention period.

Assumption 3. We will introduce flexible spline functions to account for seasonality and long-term trends. We will add a scale parameter, which will be the Pearson statistic divided by the residual degrees of freedom, to account for potential overdispersion (a violation of the Poisson regression assumption). We will test for autocorrelation using the Durbin-Watson tests and visual plots of the autocorrelation function and partial autocorrelation function. If there is evidence of autocorrelation, we will use the Newey-West method to obtain adjusted standard errors.

Therefore, in the final analysis, we will use Poisson regression to model the count data.. The final model is an extension of the regression described in equation 1 with the specifications described above. The model will include each of the interventions (either as single interventions or combinations of), denoted  $j = 1, \dots, J$ . This method allows estimating simultaneously the effect of several interventions. We will consider interventions implemented within a 7-day period as a combination of interventions, following previous studies. This means that the maximum number of combinations of interventions is 52,  $t = 1, \dots, 52$ . We will estimate the effect of the interventions separately when interventions are separated by at least seven consecutive days and for a maximum period of 30 days. The primary analysis will include a 7-day lag to account for the delay in the intervention to be effective, considering the incubation period of SARS-COV2.

$$(5) \ln(Y_t) = \beta_0 + \beta_{1j}time_{tj} + \beta_{2j}post_{tj} + \beta_{3j}timepost_{tj} + \mu_t$$

This model will be run at the municipal level and, therefore, we expect to run 10,000 regressions multiplied by the number of combinations of interventions at each municipal level. Coefficient  $\beta_{3j}$  is the coefficient of interest and represents the change in slope after the intervention  $j$  at period  $t$ .

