In coefficient of interest at a second stage, we will pool the effects for each intervention -or combination of interventions- (i.e. the coefficient of interest  $\beta_{3j}$  from the local level regression) using a random-effects meta-analysis. This meta-analysis will provide information to obtain a pooled effect estimate and a measure of heterogeneity. We will use the  $I^2$  as a measure of heterogeneity.

If the heterogeneity is moderate or high ( $I^2$  higher than 50%), we will carry out a meta-regression to assess whether subnational level determinants can explain the observed heterogeneity. We will analyse the following covariates: (i) Population size, (ii) Population density, (iii) Proportion of population over 60 years old, as a proxy for age structure of the population, (iv) Household density, and (iv) Proportion of population with basic education, as a proxy of socioeconomic status.

The meta-regression has the effect size  $\widehat{\theta}_k$  of a first-stage regression  $k$  as the outcome, covariates  $x_{ik}$ , a fixed effect  $\rho_1 S_a$  for the second-tier level  $a$  (i.e. State or Region) and a random-effect  $\delta_2 N_b$  for the national level  $b$  and a fixed effect  $\rho_2 Y$  for the time of the year (quarterly periods)(equation 6). The equation includes two types of independent errors, where  $\varepsilon_k$  is the sampling error of the effect size and  $\varsigma_k$  is the random-effect error term.

$$(6) \theta_k = \gamma_1 x_{1k} + \dots + \gamma_n x_{nk} + \rho_1 S_a + \delta_2 N_b + \rho_2 Y + \varepsilon_k + \varsigma_k$$

These controls for higher levels of administration and time of the year will allow us to control for constant characteristics at the subnational and national level, as well as changes in the effectiveness throughout the pandemic.

We will carry out the following sensitivity analyses: (1) comparison of effect estimates using a 5-day and 10-day lag; (2) quasi-myopic analyses to control for anticipatory effects (if there is evidence of), and (3) placebo tests evaluating changes at times when no policy was implemented. In the analyses for the number of cases and time-varying R, we will run additional sensitivity analyses estimating the number of SARS-CoV-2 cases corrected by under-ascertainment derived from mortality statistics.

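### The 50% I² gate on the meta-regression reflects first-stage precision rather than how much effects differ, and with the smoothed outcome it is likelier to open falsely than to close

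*Protocol*

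**What the plan says.** The Protocol's aims make the third aim conditional: "Third, assuming we find evidence of moderate to substantial heterogeneity at the local level, we aim to explore potential explanations for this heterogeneity". Its Statistical analysis section turns that into a rule: "If we observe high levels of heterogeneity (defined as higher than 50%), we will also use standard meta-regression techniques". It does not name the statistic there and labels the level high.

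The SAP (Analysis methods) names it as I², keeps the 50% level, labels it moderate or high, and then says "we will carry out a meta-regression to assess whether subnational level determinants can explain the observed heterogeneity". On what the pooling will deliver it says only: "This meta-analysis will provide information to obtain a pooled effect estimate and a measure of heterogeneity". I² is that measure. Neither document mentions τ, a prediction interval or any other trigger.

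The Protocol's Covariates section describes the second stage with no condition: "we will examine the change in heterogeneity after adjusting for several covariates at the local level".

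Four other SAP features matter because they set the first-stage SEs:
- The count outcomes are 7-day moving averages rounded to integers (Outcome definitions).
- Each effect is estimated "and for a maximum period of 30 days".
- SEs carry a Pearson scale parameter.
- Newey-West SEs are used if autocorrelation is found. No lag is given.

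**The concern.** Aims 2 and 3 ask how much policy effects vary between municipalities, and why. I² answers a different question: what share of the observed variation exceeds the reported sampling error. It moves with event counts, the overdispersion adjustment and the SE method, even when the true spread of effects is fixed. The same 50% therefore means different things for cases, deaths and the reproduction number, and for pools of large and small municipalities.

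If the gate closes wrongly, aim 3 is dropped for that pool. Equation 6 goes with it, and that is the only planned step with state, country and time-of-year terms. If the gate opens wrongly, sampling noise is reported as local heterogeneity and covariates are then searched to explain it.

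**Working it through.** The documents give no expected I², τ or SE, so there is no plan figure to reproduce. The 50% level, the 30-day window, the 7-day averaging and the SE methods come from the documents. Everything else is an assumption: τ = 0.02 per day on the log scale, 21 pre-intervention and 30 post-intervention days, a flat underlying mean, log-normal municipality sizes (log-SD 1.2), median counts of 0.1 to 5 per day, and no splines.

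**1. What the gate tests.** I² = (Q − (k − 1))/Q ≈ τ²/(τ² + SE²). It exceeds 50% only if τ > SE. This holds whatever values are assumed.

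**2. Closing on real heterogeneity (valid SEs).** τ = 0.02 per day means that one SD between municipalities multiplies daily counts by exp(0.02 × 30) = 1.82 after 30 days.
- SE 0.01: 0.0004/(0.0004 + 0.0001) = 80%
- SE 0.02: 0.0004/(0.0004 + 0.0004) = 50%
- SE 0.03: 0.0004/(0.0004 + 0.0009) = 31%
- SE 0.05: 0.0004/(0.0004 + 0.0025) = 14%

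Such SEs are plausible for unsmoothed counts. The Poisson information matrix gives an SE for the slope change of 0.019 at 5 events per day, 0.042 at 1 per day and 0.132 at 0.1 per day. In simulated pools of 1,000 mixed-size municipalities, all with τ = 0.02, mean I² was 70%, 32% and 12% at medians of 5, 1 and 0.3 per day. At a median of 5 per day, raising dispersion from 1 to 2 to 4 moved I² from 70% to 54% to 36%.

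A closed gate can discard a workable analysis. With 50 municipalities, SE 0.03 and one covariate explaining half of τ², the gate opened in 5% of runs, while the ungated meta-regression had 82% power (two-sided 5%, municipalities independent).

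**3. Opening on no heterogeneity (SEs as planned).** If reported SEs are a fraction f of the true ones and τ = 0, then I² ≈ 1 − f². So f = 0.707 gives 50% and f = 0.5 gives 75%.

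A hand approximation for the smoothing: averaging seven independent daily counts divides the residual variance by 7, and the Pearson scale falls with it. The slope change depends on slow movement in the series and keeps nearly its full sampling variance. Then f² ≈ 1/7, f ≈ 0.38, and I² ≈ 1 − 1/7 = 86%. This ignores rounding.

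Simulation of the rounded 7-day average agrees. With Pearson-scaled or Newey-West SEs, I² was 84–92% at τ = 0, which corresponds to f between √0.16 = 0.40 and √0.08 = 0.28. At τ = 0.02 it was 86–99%. The two ranges overlap, so I² barely separates no heterogeneity from material heterogeneity.

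A separate run of 400 municipalities, leaving out near-separated fits, gave these values at τ = 0:

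| Median count per day | Pearson scale | Newey-West, lag 7 |
|---|---|---|
| 0.3 | 84% | 82% |
| 1 | 86% | 85% |
| 5 | 87% | 88% |

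A lag of 14 gave 87–93%. Newey-West does not repair the problem in series of 21 + 30 = 51 days.

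**4. τ inherits the error.** For municipalities all at 1 event per day, with true SE 0.042, f² = 1/7 and τ = 0, the estimated τ would be about 0.042 × √(6/7) = 0.039 per day. That is an apparent exp(0.039 × 30) ≈ 3.2-fold spread per SD where none exists.

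**The case against.** The best defence is that the condition is deliberate. Aim 3 is worded as conditional, the threshold is fixed in advance, and a fixed rule is transparent. That stands as a reason to have a condition. It does not support I² as the condition, because the aim refers to the amount of heterogeneity and I² does not measure amount.

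A second defence is that the SAP already plans overdispersion scaling, autocorrelation checks and placebo tests. The first two are in the simulation and do not correct the SEs. Placebo tests could expose the problem, but nothing links their result to the gate. The Protocol's unconditional covariate sentence is no rescue either, since the SAP repeats the gate.

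Some stronger readings are tempting, and the documents do not support them:
- *That the gate will probably cancel aim 3, above all for deaths.* The low I² values in step 2 need valid SEs on raw counts. With the planned smoothed outcome and planned SEs, simulated I² stayed well above 50%. At 0.1 events per day the rounded average is mostly zero, and about 75–83% of fits were unusable. Such units leave the pool or carry little weight; they do not simply pull I² down.
- *That sparse data keep I² low however much effects differ.* At SE 0.05, τ = 0.06 gives 0.0036/(0.0036 + 0.0025) = 59%.
- *That small SEs let trivial differences through.* τ = 0.01 with SE 0.005 gives 80%, but exp(0.01 × 30) = 1.35-fold per SD after 30 days is not trivial.
- *That the study's size guarantees the lost analysis would be decisive.* The SAP says "we expect to run 10,000 regressions multiplied by the number of combinations of interventions at each municipal level". Large z-values from that number would assume independent municipalities and ignore the state and country terms in equation 6.

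**Conclusion.** The point holds as a flaw in the choice of trigger. That I² passes 50% only when τ exceeds the typical SE does not depend on any assumed value. The gate can close despite a 1.82-fold spread per SD (I² 31% at SE 0.03, 14% at SE 0.05) and can open with no spread at all (about 84–92%). Under the plan as written the second failure is the likelier.

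The sizes rest on assumed τ, counts and series lengths, and on models without the splines that the SAP intends to add; their effect on these figures was not examined. The simulations cover the case and death counts, not the reproduction number, although the relation in step 1 applies there too.

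Two texts also need reconciling: the unconditional covariate sentence against the gate, and the two labels for the same 50% level.

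**What to change.** 1. Remove the I² condition. Run the equation 6 meta-regression for every pooled intervention or combination that has a pre-specified minimum number of municipalities, and reword aim 3 to match.
2. Report τ on the slope scale and a 95% prediction interval as the main heterogeneity results for aim 2. Keep I² as a descriptive figure.
3. Base all of these on first-stage SEs that are valid for the serial correlation created by the moving average. One way is to model raw daily counts with day-of-week terms and keep the moving average for display. Without this step, τ and the interval are inflated as well.
4. Align the Protocol's Covariates and Statistical analysis sections with the SAP, and drop the differing labels for 50%.

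This is a cheap improvement. Items 1, 2 and 4 are wording and routine meta-analysis output. Item 3 changes the series that is modelled, but the daily data are already being collected. The downside is more exploratory meta-regressions, some in pools with little heterogeneity, and they should be labelled exploratory.

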Colombia	Instituto Nacional de Salud	https://www.datos.gov.co/Salud-y-Protecci-n-Social/Casos-positivos-de-COVID-19-en-Colombia/gt2j-8ykr
Guatemala	Ministerio de Salud Pública y Asistencia Social	https://tablerocovid.mspas.gob.gt/
Costa Rica	Observatorio Geográfico en Salud - Ministerio de Salud	http://geovision.uned.ac.cr/oges/#descargas
Mexico	Subdirector de Notificación y Registros Epidemiológicos	https://datos.gob.mx/busca/dataset/informacion-referente-a-casos-covid-19-en-mexico
Paraguay	Ministerio de Salud Pública y Bienestar Social	https://public.tableau.com/profile/mspbs#!vizhome/COVID19PY-Registros/Descargardatos
Peru	Ministerio de Salud	https://www.datosabiertos.gob.pe/group/datos-abiertos-de-covid-19

Table S2. Countries excluded from the study.

Eligible Country	Reason for exclusion	Source
Bolivia	There is weekly data available at the municipal level, but we did not find daily data.	https://datos.gob.bo/dataset/casos-covid-19-acumulado-por-municipios
Cuba	Information is available in daily reports, but we did not find open data to download.	https://salud.msp.gob.cu/
Ecuador	Daily subnational data is available in charts, but it is not open to download.	https://www.coronavirusecuador.com/data
El Salvador	Daily subnational data is available in charts, but it is not open to download.	https://covid19.gob.sv/
French Guiana	The official language is not Spanish or Portuguese.	-
Guiana	The official language is not Spanish or Portuguese.	-
Haiti	The official language is not Spanish or Portuguese	-
Honduras	Information is available in reports, but we could not find data to download.	http://www.salud.gob.hn/site/index.php/covid19
Nicaragua	We did not find an official source of information.	
Panama	There is a map and some charts with information, but data is not open to download.	http://minsa.gob.pa/covid-19
Republica Dominicana	Information is available in reports, but we did not find open data to download.	https://www.msp.gob.do/web/?page_id=6948
Suriname	The official language is not Spanish or Portuguese.	-
Uruguay	There is information on cumulative cases and deaths available, but not daily subnational data on new events.	https://catalogodatos.gub.uy/dataset/sinae01-covid19
Venezuela	There is daily data available, but it is not disaggregated at the subnational level.	https://covid19.patria.org.ve/api-covid-19-venezuela/

Table S3. Covariates used in the study and availability at the local level.

	Local level availability				
	Population size	Population density	Age structure	Household density	Socioeconomic status
Argentina	Yes	Yes	Yes	Yes	Yes
Brazil	Yes	Yes	Yes	Yes	Yes
Chile	Yes	Yes	Yes	Yes	Yes
Colombia	Yes	Yes	Yes	Yes	Yes
Costa Rica	Yes	Yes	Yes	Yes	Yes
Guatemala	Yes	Yes	Yes	Yes	Yes
Mexico	Yes	Yes	Yes	Yes	Yes
Paraguay	Yes	Yes	Yes	Yes	Yes
Peru	Yes	Yes	Yes	Yes	Yes

## Introduction

The COVID-19 pandemic is evolving quickly globally. By January 22, 2021, there were more than 112 million reported cases and more than 2.6 million deaths worldwide. Latin America is one of the worst-hit regions and accounts for 20.3% of the SARS-COV2 cases and 30% of the global deaths, despite having only 8% of the global population. The effectiveness of policies to reduce the spread of COVID-19 has been analyzed in several empirical studies. Nevertheless, few of these studies have included countries in Latin America or examined the effect heterogeneity and potential explanations for it. In this study we aim, first, to estimate the effectiveness of nonpharmaceutical interventions on SARS-COV2 transmission and COVID-19 mortality in Latin America; second, to examine the effect heterogeneity of transmission and mortality at the local level. Third, assuming we find evidence of moderate to substantial heterogeneity at the local level, we aim to explore potential explanations for this heterogeneity.

This Statistical Analysis Plan (SAP) provides an in-depth description of the statistical methods and definitions for the study analysis. More information on the rationale and data sources can be found in the Study Protocol.

## Study methods

### *Design*

The study is a natural experiment exploiting the variation in temporal and spatial implementation of nonpharmaceutical interventions (NPI) to reduce the spread of COVID-19 in Latin American local governments. The unit of analysis are third-tier subnational units (i.e. municipalities, districts, cantons). The setting is all Spanish and Portuguese speaking countries in Latin America that fulfil the inclusion criteria. We developed the plan following guidance from Gamble et al.

### *Sample size*

The study will use all available data that fulfils the inclusion criteria.

### *Timing of analyses and outcome assessments*

We will use data from the date of the first case in each country until December 31, 2020. We will use publicly available daily data for all outcomes. We will use the enforcement date on data on interventions collected from PoliMap ([www.polimap.org](http://www.polimap.org)).

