Viral spread (for both outcomes)	Total lockdown Partial lockdown (geographical, step-wise/graduated response) Curfew School closure Closure of shopping malls, gyms, churches, parks Remote work Restrictions to national/subnational mobility Prohibition of mass gatherings
Health systems response (for COVID-19 deaths outcome)	Interventions to increase testing capacity Interventions to increase the number of ICU/critical beds
Mitigation strategies (for both outcomes)	Direct social assistance (in-kind/cash) Cash transfer Withdrawal of pension funds

Comparator

In an interrupted time series analysis, the comparator is a counterfactual outcome defined as the projection of the pre-intervention trend to simulate what would have happened if the policy had not occurred (see Statistical Analysis Plan for definitions).

Outcomes

We will assess three primary outcomes. The first outcome will be the 7-day moving average of daily confirmed cases of COVID-19/SARS-CoV-2. The second outcome is the time-varying reproductive number between the current and previous period.¹⁹ The third outcome is the 7-day moving average of the daily number of deaths by COVID-19 in Latin American subnational regions. For the statistical modelling, these averages will be rounded to the nearest integer. We will consider a 7-day lag as the primary lag. Details on sensitivity analyses can be found in the Statistical Analysis Plan.

We define the outcomes following the official national sources definitions, as each country applies its criteria to define the occurrences and the deaths caused by COVID-19. It is important to note that those criteria are not always clearly stated, but all subnational units are under the same measure at each time.

Data sources

We will obtain COVID-19 cases and deaths data, as well as the covariates, on official government sources, such as the Ministry of Health and Ministry of Science and Technology (see Supplementary Appendix Table S2). The intervention information will come from legal documents, official statements, and quantitative accounts from trustable sources.

Covariates

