#### *Outcome definitions*

The first outcome will be the 7-day moving average of daily confirmed cases of COVID-19/SARS-CoV-2. The second outcome is the time-varying reproductive number between the current and previous period. The third outcome is the 7-day moving average of the daily number of deaths by COVID-19 in Latin American subnational regions. For the statistical modelling, these averages will be rounded to the nearest integer. We will consider a 7-day lag as the primary lag. We will use the definition of COVID-19 case and death which is valid at any given time in each country.

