#### *Analysis methods*

The primary analysis will use interrupted time series (ITS) for each subnational unit to examine the causal effect of COVID-19 policies on primary outcomes. Interrupted time series is a widely used tool in causal inference that allows comparing trends before and after the introduction of an intervention. The counterfactual outcome is the projection of the trend in the period before the introduction of the intervention into the time period was introduced. The unit of analysis in this study is days, starting from the date of the first case.

The standard model for an ITS regression is as follows

$$(1) Y_t = \beta_0 + \beta_1 time_t + \beta_2 post_t + \beta_3 timepost_t + \beta'_4 X + \mu_t$$

where  $time_t$  is a variable which equals one at the first time point  $t$  and increases by one after each subsequent time point;  $post_t$  is a dummy variable that equals to zero prior to the introduction of the intervention ( $p$ ) and equals one for every time point thereafter;  $timepost_t$  is a variable that equals to zero until time  $p-1$ , and increases by one for each subsequent time point; and  $X$  is a vector of covariates. Coefficient  $\beta_3$  is the coefficient of interest and represents the change in slope after time  $p$ .

The validity of the ITS rests on three assumptions. Assumption 1 states that the expectation of the pre-intervention level and trends would be the same irrespective of whether the sample received the treatment. Assumption 2 states that in the absence of treatment, the outcome of interest would remain unchanged in the post-intervention period. Assumption 3 states that the time trends in the pre and post periods can be expressed as a linear combination of parameters.

Using the potential outcomes framework, the estimated effect of a policy at time  $p$  could be defined as

$$(2) \Delta_t = Y_t(1) - Y_t(0)$$

These difference could also be expressed in terms of two equations

$$(3) Y_t(1) = \alpha_0 + \alpha_1 time_t + \alpha_2 post_t + \alpha_3 timepost_t + \varepsilon_t$$

$$(4) Y_t(0) = \theta_0 + \theta_1 time_t + \theta_2 post_t + \theta_3 timepost_t + \nu_t$$

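### For policies enforced early, zeros before the virus reaches a municipality can produce a false negative slope change, because the SAP sets no local time origin

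*SAP*

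**What the plan says.** The data window is national: "We will use data from the date of the first case in each country until December 31, 2020" (SAP, Timing of analyses and outcome assessments). The modelling section gives the time origin as "The unit of analysis in this study is days, starting from the date of the first case" (SAP, Analysis methods), without saying whether this is the country's or the municipality's first case.

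The first-stage model is local: "This model will be run at the municipal level and, therefore, we expect to run 10,000 regressions", multiplied by the number of intervention combinations. The model family is Poisson with a log link (equation 5). The target, beta3j, "is the coefficient of interest and represents the change in slope after the intervention". The protocol's comparator is "a counterfactual outcome defined as the projection of the pre-intervention trend to simulate what would have happened if the policy had not occurred", so the fitted pre-policy slope sets the counterfactual directly.

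The count outcomes are 7-day moving averages, and "For the statistical modelling, these averages will be rounded to the nearest integer" (SAP, Outcome definitions). The lag is 7 days and each effect is followed for at most 30 days. If autocorrelation is found, "we will use the Newey-West method to obtain adjusted standard errors". Splines for seasonality and long-term trend are planned without type, knots or degrees of freedom. Under Sample size, all available data meeting the inclusion criteria are used. Neither document sets a local start, a minimum count, a minimum number of non-zero pre-policy days, or a rule for a pre-policy period that is entirely zero.

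**The concern.** On the day of a country's first case, almost every other municipality has none. If its series still starts that day, it opens with zeros that reflect when the virus arrived, not how fast it spread. A log-linear pre-policy trend fitted through zeros and then cases is steeper than the true local growth. Continued growth at an unchanged rate then looks like a slowdown after the policy.

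At stake is the primary coefficient. An early policy with no effect could look beneficial, by an amount that depends on local arrival date. Without splines the error always has the same sign when arrival precedes the lagged policy date, so pooling over municipalities does not cancel it.

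**Working it through.** The documents give no bias or power figure here, so there is none to reproduce. The question is what equation 5 returns when the policy does nothing.

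**From the SAP:** Poisson log link; time, post and timepost terms; 7-day lag; 30 post-policy days; 7-day average.

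**Assumed:** one policy enforced on day 21 after the country's first case (lagged date 21 + 7 = 28); growth g = 0.06/day after local arrival; true effect zero; noise-free means; a trailing, unrounded average; no splines.

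**Step 1. Formula.** With one policy, post and timepost are free, so the days before and after the lagged date are fitted separately:

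beta3 = (post slope) - (pre slope) = g - b, where b is the fitted pre-policy slope.

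The Poisson score equations make b match the case-weighted mean day:

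sum(t·e^(bt)) / sum(e^(bt)) over days 1 to 27 = sum(t·y) / sum(y).

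**Step 2. One case in full.** With arrival on day 14 and daily counts, cases fall on days 14 to 27 and their weighted mean day is 21.46. A slope of 0.06 over days 1 to 27 would give a mean day of only 17.49; reaching 21.46 needs b = 0.155. So beta3 = 0.060 - 0.155 = -0.095/day. Over 30 days the slope change alone implies a ratio of exp(-30 × 0.0954) = 0.06 to the projected trend, from a policy that did nothing.

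**Step 3. Other arrival dates and the planned outcome.**

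| Local arrival | Daily counts, country start | 7-day average, country start | 7-day average, start at local first case | 7-day average, start at first full window |
|---|---|---|---|---|
| day 7 | -0.033 | -0.053 | -0.026 | 0.000 |
| day 14 | -0.095 | -0.132 | -0.064 | 0.000 |
| day 20 | -0.212 | -0.305 | -0.190 | 0.000 (2 pre-policy days only) |

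A bare local start gives 0.000 on daily counts but not on the averaged outcome, because the first six averages still include pre-arrival zeros.

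**Step 4. Later policies** (arrival day 20, daily counts, country start): beta3 is -0.212 at lagged policy day 28, -0.015 at day 60, -0.003 at day 90 and -0.0001 at day 150.

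**Step 5. With noise and rounding.** Assume Poisson counts, rounded averages, 5 cases/day at arrival, g = 0.05, lagged policy day 45 and no effect. The median beta3 under a country start is -0.036, -0.083 and -0.232 for arrival on days 15, 25 and 35. Random-effects pooling of 300 units with arrival spread over days 1 to 38 gives:

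- country start: -0.061 (95% CI -0.065 to -0.057);
- bare local start: -0.033 (-0.036 to -0.030);
- first full window: -0.001 (-0.003 to +0.001), with 270 of the 300 units usable.

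**Step 6. Splines.** In the Step 5 setting with arrival on day 25, the country-start beta3 of -0.083 becomes +0.110 with 4 df and about 0 with 6 df; at 6 df, 44% of null runs are still significant. In the Step 1 setting on daily counts with arrival on day 14, a natural cubic spline gives +0.106, -0.247 and -0.065 with 4, 5 and 6 df.

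**Step 7. Arrival after the lagged policy date.** Every pre-policy value is zero, so b has no finite estimate and beta3 is not identified. The standard error depends on the computation: above 300 model-based; 0.05 to 0.13 for Newey-West from influence functions; about 0.5 to 6 by direct inversion of the sandwich; and, in one standard routine, undefined in 45 to 54% of runs with a median of about 14 otherwise. In inverse-variance terms, 0.1 gives 1/0.01 = 100 and 14 gives 1/196 = 0.005, before between-unit variance is added.

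**The case against.** **The national start is a data window, not a model clock.** The sentence in Analysis methods sits in a paragraph about fitting each subnational unit and could mean the local first case. This stands in part: a reader might infer that every series certainly starts at the country's first case, and the text does not settle that. But the only sentence that names a level names the country. A local first case would still leave the averaging ramp-up (-0.026 and -0.064 in Step 3), and for deaths it would leave zeros between the first local case and the first local death.

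**The final model includes splines.** This limits what can be said about size and sign. The figures without splines cannot be presented as what the plan will produce. Step 6 shows, however, that splines are not a dependable cure, and equation 5 shows no spline term.

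**Other safeguards exist.** Newey-West changes the standard error and leaves the coefficient alone. The quasi-myopic analysis addresses anticipation. Placebo tests might flag false slopes, but no action follows from them.

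**Stronger readings that a reader might infer.**

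- *All-zero pre-periods push the pooled estimate upward with substantial weight.* One way of computing the standard error gives that result; others give them almost no weight. What is supported is non-identification with no handling rule.
- *The artefact inflates I² and mimics effects of population size or density.* This is plausible but not shown. In simulation I² was about 0.9 under the country start and the full-window start alike, and no covariate link was computed.
- *All policies are affected.* Step 4 contradicts this.

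**Conclusion.** The point holds for policies enforced early relative to local arrival. As written, the plan allows pre-arrival zeros into the municipal fits, and these alone can generate an apparent benefit. Under equation 5 without splines, with growth of 0.06/day and a lagged policy on day 28, the false beta3 is about -0.03 to -0.21/day on daily counts and -0.05 to -0.31/day on the 7-day average. By policy day 90 it is negligible for arrival on day 20.

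The mechanism follows from the model. The magnitudes are illustrative, because the documents give no arrival dates, policy dates or growth rates. With splines, both size and sign are open until the degrees of freedom are stated. The time-varying reproduction number, the second primary outcome, was not examined. Since the bias falls on the primary coefficient and the remedy is a data filter, it should be corrected before the first-stage models are run.

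**What to change.** In the SAP, under Timing of analyses and Analysis methods, state one local time origin:

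1. Start each municipality's series on the first day with a complete 7-day averaging window after its own first confirmed case (first death for the deaths outcome).
2. Estimate beta3j only where a pre-specified minimum lies between that start and the lagged policy date, for example 14 days of which at least 7 are non-zero. These thresholds are a suggestion; the documents imply none. Count non-zero days on the rounded series, where fewer than 4 cases in 7 days rounds to 0 (3/7 = 0.43; 4/7 = 0.57).
3. Treat all-zero or too-short pre-periods as non-estimable, leave them out of the pool for that intervention, and count them in the flow diagram already planned under Study population.
4. As a sensitivity analysis, fit those areas at the second-tier level.
5. State the spline type, knots and degrees of freedom.

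The cost is SAP wording and a data filter, plus some loss of information. With a lagged policy on day 28, arrival on day 7 starts the series on day 13 and leaves 28 - 13 = 15 pre-policy days, so it is kept. Arrival on day 14 starts it on day 20 and leaves 8, so it is dropped under a 14-day minimum. Fewer, earlier-hit municipalities would therefore inform the earliest policies, and pooled results should be described that way. A small residual bias can remain: with the 14/7 rule and full window, one simulation starting at 0.5 cases/day left a pooled beta3 of about +0.007 on rounded averages.
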